5.3 Covariate Analyses

The prospective participants and historical controls in the study may differ in ways other than the interventions or exposures under investigation. Covariates will be used to adjust the regressions prespecified in the primary analysis for potential differences between the control and prospective arms, and in derivation of propensity scores used to adjust for biases between the two arms, either by weighting subjects in the alternative analysis or by matching subjects in exploratory analyses..

The following variables are candidates for inclusion as covariates in the primary analysis: regression with covariates. These baseline covariates are present before blood draw.

- Maternal age
- Categorical parity: multiparous vs. nulliparous
- Maternal substance use disorders assessed as Neonatal Opioid Withdrawal Syndrome

The following variables are candidates for inclusion as covariates in the alternative analysis using inverse probability score weighting, and in the exploratory analysis using propensity matching. These baseline covariates are present before blood draw.

- Maternal age
- Categorical parity (nulliparous vs. multiparous)
- Gravidity (integer)
- Number of term children
- Number of miscarriages
- Maternal race
- Pre-pregnancy continuous BMI
- Pre-pregnancy categorical low BMI<19
- Maternal height
- Maternal chronic hypertension
- Gestational diabetes
- Insurance status
- Smoking status
- Maternal substance use disorders assessed as Neonatal Opioid Withdrawal Syndrome
- Delivery outside of ChristianaCare

Inclusion of covariates in the covariate-adjusted primary, alternative and exploratory analyses will depend on the proportion of missing values for the covariate, as follows. For each candidate variable, if fewer than 1% of subjects have a missing value, that variable will be included as a covariate in the analysis. Sensitivity of results to missing data will be examined using missing data analysis methods.

The primary and alternative analyses will use cases with complete data for the included covariates, provided that no more than 5% of the total subjects are excluded from the analysis. If more than 5% of the total subjects would be excluded from the analysis,

candidate variables will be dropped from the analyses in order of the percent missing, until no more than 5% of the total subjects are excluded from the analysis.

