The propensity score model will be derived from logistic regression using the key clinical covariates available at the gestational age of PreTRM® blood draw in the historical cohort, as well basic demographic characteristics. The variables used to generate propensity scores are specified above.

The performance of the propensity score model will be evaluated by AUC/ROC c-index; potential interaction terms or high degree of terms may be included to improve the performance of the propensity model. We will obtain an estimation for the propensity score: predicted probability (p).

With propensity score methods, we will check whether covariates are balanced across the prospective and historical cohorts. We can examine the distribution of propensity score between groups. We will assess covariate balance between groups using p-value for comparison of two group, as well absolute standardized mean difference (ASMD), with an ASMD <0.1 indicating good balance.

We propose Inverse Propensity score Weighting (IPW) method for the alternative analysis. IPW is a statistical technique for calculating statistics standardized to a pseudo-population different from that in which the data was collected. After obtaining propensity score, we define for the prospective arm:

$$IPW = \frac{1}{PS}; \quad IPW = \frac{1}{PS}; \quad \text{for historical controls: } IPW = \frac{1}{1-PS}.$$

$IPW = \frac{1}{1-PS}$. To avoid the IPW method's instability to extremes of propensity among participants with high propensity score weights with undue influence the results, we will use truncated scores and weights: 1) below the 1st or 5th percentile and above the

99th or 95th percentile; resulting in weights between reasonable intervals for all participants; 2) truncating propensity score <0.001 or >0.999.

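### The propensity model is judged and extended by its c-index, which measures separation of the arms rather than control of confounding, and no rule gives ASMD precedence over p-values

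*SAP*

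**What the plan says.** SAP Section 5.3 builds the propensity score by logistic regression of arm on baseline covariates. On variables it says "The variables used to generate propensity scores are specified above", which points to a list of 15 candidates; calendar time is not among them. On the criterion and on extending the model it says "The performance of the propensity score model will be evaluated by AUC/ROC c-index; potential interaction terms or high degree of terms may be included", the stated purpose being to improve that performance. It names no particular terms and no point at which to stop.

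The next paragraph turns to balance: "We will assess covariate balance between groups using p-value for comparison of two group", and alongside it "absolute standardized mean difference (ASMD), with an ASMD <0.1 indicating good balance". Nothing says which of the two decides, or that a failed check leads back to the model. The section then truncates scores and weights, at the 1st/99th or the 5th/95th percentile and at scores below 0.001 or above 0.999, because it expects instability from extreme propensities.

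Section 5.4 makes the weighted regression the alternative analysis and the matched analysis exploratory. It compares the direction of effect across four methods and adds a doubly robust analysis if directions differ. Table 2 in that section lays out baseline characteristics by method with p-value columns and no ASMD column.

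**The concern.** A propensity score is there to make the arms comparable on covariates. A high c-index means the opposite of easy comparability: the arms overlap little. It rises most readily through terms that separate the two cohorts, whether or not those terms bear on neonatal outcome. The only model-building rule in Section 5.3 therefore aims at separation, and the one numerical balance threshold is not connected to it.

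The p-value is a poor second criterion because it depends on sample size. Before weighting, with about 10,000 controls, it flags small differences. After weighting, it can lose significance only because the weights have reduced the effective sample.

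At stake is how informative the prespecified adjustment for selection bias is in a non-randomised comparison. A needlessly noisy weighted estimate is more likely to differ in direction from the primary result by chance, or to agree with it uninformatively.

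**Working it through.** The SAP gives no c-index, effective sample size or standard error for the weighted analysis, so there is no figure of its own to reproduce on this point. The values of c below are assumptions.

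**1. The two balance criteria before weighting.** Arm sizes are 1,453 and about 10,000 (SAP Section 4). For a standardised difference, z = ASMD / √(1/1,453 + 1/10,000) = ASMD / 0.02808.

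| ASMD | z | two-sided p | ASMD rule |
|---|---|---|---|
| 0.055 | 1.96 | 0.05 | good |
| 0.08 | 2.85 | 0.004 | good |
| 0.10 | 3.56 | 0.0004 | at the limit |

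Between about 0.055 and 0.1 the criteria disagree.

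**2. From c-index to effective sample size.** The prospective mITT size is derived from Section 4, with 34% screen-positive and 55% compliance taken as the share who consented and started treatment: 1,453 × (0.66 + 0.34 × 0.55) = 1,453 × 0.847 = 1,231. The ratio is r = 10,000/1,231 = 8.12. Assume the linear predictor is normal with equal variance in both arms (binormal), so that d² = 2[Φ⁻¹(c)]². For weights 1/PS, the Kish effective fraction of the prospective arm is (1+r)² / (1 + 2r + r²·exp(d²)), and the standard error factor is one over its square root.

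| c | d² | exp(d²) | fraction | effective n | SE factor |
|---|---|---|---|---|---|
| 0.60 | 0.128 | 1.137 | 83.2/92.3 = 0.902 | 1,110 | 1.05 |
| 0.70 | 0.550 | 1.733 | 83.2/131.6 = 0.632 | 778 | 1.26 |
| 0.80 | 1.417 | 4.123 | 83.2/289.3 = 0.288 | 354 | 1.86 |

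At c = 0.80 the control arm keeps an effective 9,638, by the same formula with r inverted. The factor for the difference between arms is √[(1/354 + 1/9,638)/(1/1,231 + 1/10,000)] = 0.0541/0.0302 = 1.79.

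**3. With truncation, c = 0.80.** The same model was simulated (400 replicates) to give the prospective-arm SE factor:

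- weights truncated at pooled percentiles: 1.29 (1/99) and 1.06 (5/95)
- weights truncated within arm: 1.57 and 1.37
- scores truncated at pooled percentiles: 1.78 and 1.65
- fixed limits 0.001/0.999 alone: 1.84

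The strongest truncation costs balance. Pooled 5/95 weight truncation left an ASMD of 0.17 on the linear predictor even at c = 0.60. The reason is simple: the top 5% of 11,231 weights is 562, and since the large weights are nearly all prospective, that caps about 562/1,231 = 46% of that arm.

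**4. The p-value after weighting.** At the effective sizes in step 2 for c = 0.80, an ASMD of 0.10 gives z = 0.10/0.0541 = 1.85, p = 0.06. A covariate that does not meet the ASMD rule would pass the p-value, the reverse of step 1.

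**5. What extending the listed covariates alone might do.** In a simulation with 15 covariates of assumed modest effect, adding all 15 squares and 105 pairwise products as pure noise raised c from 0.59 to 0.63 and the SE factor from 1.04 to 1.11 (1.09 with 1/99 within-arm truncation). The higher c here reflects nothing about confounding.

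**The case against.** The best defence is that the plan already holds the needed pieces. ASMD below 0.1 sits in the same sentence as the p-value and is the only numerical balance threshold. Truncation is written in precisely because extreme weights were foreseen. The wording on extra terms is permissive and sets no target c. Section 5.7 chooses the matching method partly by balance. Both arms come from one hospital network with similar criteria, so c may be near 0.60, where the cost is about 5%. All of this stands and limits the size of the point. It does not supply a rule that selects model terms by balance, and choosing a matching method is not choosing the terms in the score.

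Three stronger readings are tempting, and the SAP does not support them:

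- **That balance is judged by p-values alone.** It is not; the fault is two criteria without precedence.
- **That new variables marking study period may be brought in to raise the c-index.** Section 5.3 fixes the variable list; only interactions and powers of listed covariates may be added. One listed item, "Delivery outside of ChristianaCare", might mainly predict arm, but that is inference and the SAP gives no figure for it.
- **That the weighted analysis will be badly inflated.** Inflation is possible, not established. Step 5 shows that noise terms alone do little; a large cost would need strong real separation of the arms, and the truncation chosen would change it.

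**Conclusion.** The criterion stated for the propensity model is the wrong one, and the balance check that should govern it has no defined role in choosing terms. The conflict between p-value and ASMD follows from the SAP's own arm sizes: they disagree from about 0.055 to 0.1 before weighting.

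The variance cost cannot be determined from the SAP. It runs from about 5% on the prospective-arm standard error at c = 0.60 to 80% or more at c = 0.80 untruncated, and from 6% to 78% at c = 0.80 across the percentile truncations examined. These figures rest on the binormal model, the assumed c values and the derived 1,231.

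A reader might infer that the main result is at risk. It is not: the primary covariate regression and its Holm testing do not use the propensity score. The point concerns the alternative and matched analyses and is worth correcting because the correction is free.

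**What to change.** In SAP Section 5.3, replace the c-index sentence with a balance rule:

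- Start from the prespecified covariates.
- Add an interaction or higher-order term only when a covariate's weighted (or, for matching, matched) ASMD is 0.1 or more.
- Stop when all are below 0.1. If that cannot be reached, report the remaining imbalance.
- Report the c-index and the effective sample size of each arm as descriptions of overlap only.
- Remove the p-value as a balance measure there, and put ASMD in place of the p-value columns in Table 2 (Section 5.4).
- Check ASMD after the truncation that is actually applied, and name that truncation.

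The cost is a change of SAP wording and one table shell. It needs no new data and leaves the primary analysis as it is.

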5.4 Primary and Alternative Analyses

The primary and alternative analyses will be performed in the modified ITT (mITT) population on the primary, secondary and exploratory endpoints.

The primary analysis is regression with covariates as specified for each endpoint.

The alternative analysis is regression with covariates as specified for each primary, secondary and exploratory endpoint, with weighting by inverse propensity score to address potential selection bias.

Propensity-matched and unadjusted “raw” analyses are pre-specified as exploratory analyses. These analyses will be performed on primary and secondary endpoints.

In analysis combining primary, alternative and exploratory analyses, we will present the demographic and baseline characteristics differing between the prospective arm and historical controls, selected from among the covariates prespecified for the primary and alternative analyses. We will compare the primary analysis using prespecified covariates, the alternative analysis using IPW, and exploratory PSM un-adjusted (raw) data analyses (Table 2). The results from these four distinct methods are expected to show similarity in direction and potentially in magnitude of effect. If differences in direction are observed, further analysis such as double robust propensity score analysis will be conducted.

Variable	Covariate Regression			Inverse Probability Weighted			Matched data			Unadjusted “Raw” data		
	Prospective (N=)	Historical (N=)	p-value	Prospective (N=)	Historical (N=)	p-value	Prospective	Historical	p-value			
Age												
Parity												

Table 2: Baseline Characteristics

For pre-specified analysis populations and for subgroups specified under Subgroup Analyses below, analyses will be conducted to examine the clinically important groups and unbalanced variables between the prospective and historical cohorts.

5.5 Primary Endpoints

Co-Primary Endpoint: neonatal morbidity and mortality (NMI)

Reduction in composite neonatal morbidity and mortality (NMI)(14; PREGNANT trial) in prospective subjects versus controls will be evaluated by test of proportions of NMI of ≥ 3 vs. other scores. The null hypothesis (H_{01}) is no difference between controls and the prospective arm. The alternative hypothesis is (H_{a1}) relative reduction in proportion of NMI of ≥ 3 in the prospective arm as compared to controls. Statistical testing for this endpoint will be performed using ordinal logistic regression model with covariates with weighting of NMI by NMI level value plus a constant such as 0.01.

The primary hypothesis is:

H_0 : no difference between controls and the prospective arm

Odds of a higher vs. lower NMI in the prospective arm = Odds of a higher vs. lower NMI in historical controls

H_A : relative reduction in odds of a higher vs. lower NMI in the prospective arm as compared to historical controls.

Co-Primary Endpoint: length of neonatal hospital stay

Reduction in length of neonatal hospital stay for all admissions from time of birth up to neonatal discharge in prospective subjects versus controls will be evaluated using a time-to-event analysis in the top quantile of length of stay. To avoid significant contamination of short stays associated with term births, the strata will be adjusted by the preterm birth rate. If 1.2 times the preterm birth rate in the controls is less than 10%, the quantile will be set at 1.2 times the preterm birth rate. Otherwise the quantile will be set to 10%. The null hypothesis (H_{02}) is no difference between controls and the prospective arm. The alternative hypothesis (H_{a2}) is shorter length of stay in the prospective arm as compared

to controls. Statistical testing for this endpoint will be performed using a Cox proportional hazards regression model with covariates.

The primary hypothesis is:

H_0 : no difference between controls and the prospective arm

 NNOLOS in prospective arm =

 NNOLOS in historical controls

H_A : shorter NNOLOS in the prospective arm

 as compared to historical controls.

Specification of the co-primary endpoint of NNOLOS includes adjustment for non-proportionality. In case of significant non-proportionality remaining after the adjustment prespecified above, we will undertake additional exploratory analyses in the context of the Cox model. We will stratify any covariates with non-proportional effects and incorporate the covariates into the model as stratification factors rather than predictors; this includes discretizing quantitative variables. We will document any non-linear effects of continuous covariates associated with non-proportional effects. Further, we will partition the time axis to analyze if the proportional hazards assumption holds for specific time periods (say the first week vs. after the first) but not for the entire length of hospital stay.

Holm's method will be used to control for multiple hypothesis testing (H_{01} vs H_{a1} , H_{02} vs H_{a2}) of the co-primary endpoints in the study, controlling the family-wise error rate, to a significant α -level of < 0.05 .

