From historical data on pregnancies at ChristianaCare Health System, we estimated a historical preterm birth rate of 9.1%. The sample size estimation is based on simulations of co-primary outcomes based on a simulated distribution of gestational age with a singleton preterm birth rate of 9.1%, and an effect of intervention based on literature data²⁶⁻²⁸, with α -level spending of 0.05 shared between co-primaries using Holm's method.

Given shut-down of the study due to the SARS-CoV-2 pandemic, the sample size for the study is estimated to be approximately 1,453 subjects in the prospective arm, and approximately 10,000 in the historical control group. In the primary and alternative analyses, more than 10,000 subjects may meet the eligibility criteria for the historical control group and have the required data, and if so, they will be included in the study.

Power and sample size for this study are affected by factors including the proportion of prospective subjects receiving PreTRM® risk scores at or above the threshold of 16% risk (the study Screen Positive Rate (SPR)), the proportion of higher-risk subjects complying with interventions (compliance), and the rate at which subjects and their neonates remain in the study (retention). For the purpose of power and sample size estimation and based on study monitoring, we estimate that 34% of subjects in the pre-pandemic portion of the prospective arm had PreTRM® risk scores at or above the threshold of 16% risk (the SPR).

Power and sample size are also affected by the study population's baseline level of risk of adverse neonatal outcomes related to prematurity, the sensitivity of testing in identifying at-risk pregnancies, retention of subjects in the study and the efficacy of the interventions as implemented in the study. Literature²⁶⁻²⁸ indicates that the effect of treatment is not constant across different values of GAB. Thus, there is no single value of the effect size in terms of proportion of subjects with NMI less than 3, or mean length of stay. Rather, the effect size is larger for subjects with earlier GAB, while the effect size is reduced for subjects with later GAB.

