For these reasons, power and sample size were estimated based on simulations, using a range of possible values for the factors noted above. These simulations used the observed distribution of GAB from previous studies, adjusted to match the expected overall preterm birth rate of 9.1% in this study. Treatment effect was modeled as a shift in the GAB corresponding to the effect sizes reported in published studies of preterm birth prevention that were based on single treatment modalities, and with extrapolated treatment effects estimating additive effects of bundled interventions.

For the first co-primary endpoint, reduction of severe composite morbidity/mortality, a range of the possible expected effect size can be inferred from the simulations. In the simulations, the proportion of subjects with NMI ≥ 3 is expected to be between 0.023 and 0.02 in the prospective arm and near 0.036 in the control arm based on a previous clinical utility study (Sera Prognostics: data on file). Assuming these proportions, a one-

sided Fisher's Exact test, a sample size of approximately 1,453 subjects with outcomes in the prospective arm with 55% compliance among higher risk subjects and about 10,000 historical controls provides power of 0.7 – 0.9 (NCSS PASS 2020, module "Group-Sequential Tests for Two Proportions").

For the second co-primary test, length of neonatal hospital length of stay from time of birth up to neonatal discharge is assessed by Cox proportional hazards regression with stratification. The hazard ratio based on simulations is expected to be between 1.32 and 1.46 based on a previous clinical utility study (Sera Prognostics: data on file). Assuming these hazard ratios, a sample size of approximately 1,453 subjects with outcomes in the prospective arm with 55% compliance among higher risk subjects and about 10,000 historical controls provides power of 0.8 – 1.0 (NCSS PASS 2020, modules "Group-Sequential Tests for Two Hazard Rates" and "Tests for Two Survival Curves Using Cox's Proportional Hazards Model"). Stratification is indicated based on non-proportionality observed in previous studies.

The two co-primary endpoints provide independent measurements of improved neonatal outcomes. Due to their correlation, there may be modest power to be gained from having two co-primary endpoints. The estimated study power for the combination of the two co-primary endpoints is 0.8 – 1.0.

5 Statistical Analysis

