Statistical tests will be performed at the 5% significance level unless otherwise specified. Such tests will be two-tailed unless otherwise specified as directional tests. Primary and secondary endpoints will be analyzed using one-tailed tests.

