As an exploratory analysis, a test of the proportional odds assumption for NMI data will be conducted. If the proportional odds assumption does not hold, we will examine the data using a set of separate logistic regressions or partial proportional odds models, to explicitly see how the odds ratios for the explanatory variables vary at the different thresholds. Alternatively, we will also apply the generalized logit model, which treats the response as nominal (unordered) rather than ordinal and has a full set of parameters for each generalized logit. We will then compare the results from proportional, fully nonproportional, and partial proportional odds models fitted to data.

As exploratory analyses, the primary analysis will be replicated, with the modification that the analysis will be restricted to prospective subjects with at least one propensity-matched control, and historical controls will be restricted to those propensity-matched to prospective subjects. At most 4 historical controls will be matched to each prospective subject. Matching algorithms will be chosen from among nearest neighbor matching, caliper matching with comparison units within a certain width of the propensity score of the treated units get matched, where the width is generally a fraction of the standard deviation of the propensity score; Mahalanobis metric matching in conjunction with propensity score matching (PSM), stratification matching, difference-in-differences matching (kernel and local linear weights), or exact matching. The matching method will

be chosen by the distribution of the propensity scores and the balance status of baseline characteristics.

As exploratory analyses, the primary and alternative analyses will be replicated using the ITT population. Subjects with missing data for required variables will be excluded from the analyses. To test if covariates are known to be misclassified under some approaches, an “intention to treat” analysis will be conducted that assumes that each participant continues to be exposed once they have received an initial treatment. Originally used in the analysis of randomized trials, this approach has been used in this hybrid study. It can be worthwhile to do a sensitivity analysis on studies that use an “intention to treat” approach to see how different an “as treated” analysis would be even if intention to treat is the main estimate of interest.

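### The NMI co-primary model weights each infant by its own outcome, with an open constant and no stated variance, so its type I error is not assured and it is not the NMI ≥ 3 comparison that was powered

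*SAP*

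**What the plan says.** SAP Section 5.5 describes the NMI co-primary endpoint in three ways.

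- It first names a test of proportions for NMI ≥ 3 against lower scores. H_a1 is a "relative reduction in proportion of NMI of ≥ 3 in the prospective arm as compared to controls". The Holm procedure at the end of Section 5.5 refers to this H_01/H_a1 pair.
- It then says that the test will be an "ordinal logistic regression model with covariates with weighting of NMI by NMI level value plus a constant such as 0.01".
- It then sets out a primary hypothesis in different terms, a "relative reduction in odds of a higher vs. lower NMI in the prospective arm as compared to historical controls".

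The power statement in Section 4 concerns a one-sided Fisher's exact test on the proportion with NMI ≥ 3, "expected to be between 0.023 and 0.02 in the prospective arm and near 0.036 in the control arm", and gives power of 0.7–0.9. The opening of Section 5 adds: "Primary and secondary endpoints will be analyzed using one-tailed tests".

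Section 5.7 contains the only check on the ordinal model: "As an exploratory analysis, a test of the proportional odds assumption for NMI data will be conducted". No section fixes the constant, says whether the weights are rescaled, or names a variance estimator for this test.

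**The concern.** The weight is a function of the infant's own outcome. Ordinary model-based standard errors treat a weight of 3.01 as about three independent infants, so the variance is understated and type I error rises. A robust variance largely repairs this, but the plan does not ask for one, and software defaults would decide. Holm's method protects the family-wise error only if each p-value entering it is valid.

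The estimand is a separate problem. With a constant near 0.01, infants with NMI 0 carry almost no weight. The model then mainly compares severity among affected infants, which is neither the NMI ≥ 3 proportion nor the ordinary odds of a higher score. The published power therefore does not describe the test to be run, and a trial that prevented affected births across the board could miss its endpoint.

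**Working it through.** **Inputs from the SAP.** P(NMI ≥ 3) is 0.036 in controls and 0.023 or 0.020 in the prospective arm. There are 1,453 prospective subjects and about 10,000 controls, a screen-positive rate of 34% and compliance of 55%. Tests are one-sided, with family-wise alpha 0.05 under Holm, so the first step is 0.05/2 = 0.025. If compliance stands for consent and initiation, the mITT prospective arm is about 1,453 × (0.66 + 0.34 × 0.55) = 1,231.

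**Assumed.** The SAP gives no full NMI distribution. Three were used for levels 0–4, each with P(NMI ≥ 3) = 0.036:

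- 0.85/0.055/0.059/0.031/0.005
- 0.88/0.04/0.044/0.031/0.005
- 0.92/0.02/0.024/0.031/0.005

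**1. The plan's own power.** Exact one-sided Fisher power at 0.025 is 0.753 (0.036 v 0.023) and 0.925 (0.036 v 0.020) with 1,453 prospective subjects. With 1,230 it is 0.679 and 0.877. The stated 0.7–0.9 is reproduced for the unweighted NMI ≥ 3 comparison.

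**2. What the weights do.** Let w = NMI level + c. With c = 0.01 the weights are 0.01, 1.01, 2.01, 3.01 and 4.01. Under the second distribution the mean level is 0.04 + 2 × 0.044 + 3 × 0.031 + 4 × 0.005 = 0.241, so the mean weight is 0.241 + c. The share of total weight carried by NMI 0, who are 88% of infants, is 0.88c/(0.241 + c):

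| c | Share of weight at NMI 0 |
|---|---|
| 0.01 | 0.0088/0.251 = 3.5% |
| 0.1 | 0.088/0.341 = 26% |
| 1 | 0.88/1.241 = 71% |

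**3. Type I error.** The weighted cumulative-logit model was fitted to 2 × 5 tables. The Wald z used either the inverse-information (model-based) or the sandwich (robust) variance. There were 4,000 null replicates per scenario; ranges span the three distributions and both arm sizes.

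| Analysis | Nominal 0.025 | Nominal 0.05 |
|---|---|---|
| Weighted, c = 0.01, model-based | 9.1–10.0% | 13.5–14.1% |
| Weighted, c = 0.01, robust | 2.9–3.8% | 5.6–6.8% |
| Weighted, c = 0.1, model-based | 7.1–7.9% | – |
| Weighted, c = 1, model-based | 11.5–14.5% | – |
| Unweighted ordinal | 1.8–2.9% | – |
| Logistic, NMI ≥ 3 | 1.8–2.5% | – |

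As a cross-check, the null z with c = 0.01 and model-based variance had SD 1.45–1.50. At the midpoint, 1 − Φ(1.96/1.475) ≈ 9.2%. Separate runs of 1,500 replicates at 1,453 v 10,000, under the second and third distributions, gave 10.4–10.7% model-based and 3.3–3.7% robust. When the weights were rescaled to sum to the sample size, which the plan also leaves open, model-based rejection was about 27%.

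**4. What is estimated.** Take the second distribution and a true common odds ratio of 0.588, which lowers P(NMI ≥ 3) to 0.0215, the midpoint of the SAP's two rates. The weighted odds ratio is 0.95, 0.88, 0.66 and 0.59 for c = 0.001, 0.01, 0.1 and 1. The reported effect therefore depends on the open constant. As an illustration only, if NMI 1–2 fell by 36% and severe cases did not change, the weighted log odds ratio at c = 0.01 would be +0.28 to +0.32: benefit would read as harm.

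**5. Power.** NMI ≥ 3 falls from 3.6% to 2.3%, a cut of 1 − 0.023/0.036 = 36%. One-sided 0.025, c = 0.01, 2,000 replicates per scenario, in percent:

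| Pattern of benefit | Weighted, model-based | Weighted, robust | Unweighted ordinal | Logistic NMI ≥ 3 |
|---|---|---|---|---|
| Uniform 36% cut | 16–21 | 7–9 | 97–100 | 67–77 |
| Proportional odds | 20–24 | 9–12 | 96–100 | 67–77 |
| Cuts of 10/20/36/36% in levels 1–4 | 49–66 | 28–42 | 74–91 | 68–77 |
| Levels 3–4 only, moved to 0 | 70–83 | 47–66 | 26–43 | 66–76 |
| Severe moved evenly to 0/1/2 | 88–92 | 71–78 | 8–11 | 68–76 |

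The model-based column includes the inflated type I error.

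**The case against.** Several points can be made for the plan, and some stand.

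- **Case weights are an inference.** True, but it is the only reading that gives the constant a function. If category scores were meant, a cumulative-logit fit ignores them and the sentence does nothing.
- **An ordinal model matches the odds-based hypothesis.** Section 5.5 does label that statement primary, so NMI ≥ 3 is one of two stated hypotheses. It is, however, the one tied to Holm and the only one powered. At a small constant the weighted model does not estimate the ordinary odds ratio either.
- **A larger constant removes the distortion.** At c = 1 the weighted odds ratio is close to the true one under proportional odds. Model-based type I error at c = 1 is still 11.5–14.5%, and the plan's example points to a small constant.
- **A robust variance solves the alpha problem.** Mostly. The residual 2.9–3.8% reaches about 1.5 times the nominal 2.5%, and the plan does not specify it.
- **Emphasis on severity may be deliberate.** Section 4 expects that "the effect size is larger for subjects with earlier GAB, while the effect size is reduced for subjects with later GAB". When benefit is confined to levels 3–4, the weighted test does beat the unweighted ordinal model. This is a fair reason not to make the unweighted ordinal model the default replacement.
- **Section 5.7 offers separate logistic regressions if proportional odds fails.** These are conditional and exploratory, and they leave the weights in the primary test.

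**Conclusion.** The concern holds. As written, the co-primary NMI test has an undefined constant, an undefined variance and a target that matches neither stated hypothesis at the suggested constant. Its actual one-sided error at nominal 0.025 is about 9–10% with raw weights and model-based standard errors, and about 3–4% with a robust variance. Its power runs from 7–9% to 71–78% (robust), depending on where the benefit falls, while logistic regression of NMI ≥ 3 stays at 66–77% throughout. The stated 0.7–0.9 is correct for Fisher's test on NMI ≥ 3 but not for the planned analysis.

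The defect is visible in the text and needs no simulation. The figures depend on the assumed NMI 0–2 frequencies and benefit patterns, and covariates were not simulated. Null inflation with model-based standard errors appeared under every distribution tried.

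**What to change.** Delete the outcome weighting from Section 5.5. Test H_01 by covariate-adjusted logistic regression of NMI ≥ 3 against < 3, one-sided, with the variance method stated. Restate the second pair of hypotheses as odds of NMI ≥ 3, so that hypothesis, Holm family, test and power calculation agree. Report unweighted proportional-odds regression of NMI 0–4 as supportive only, because it loses power when benefit is confined to the severe levels.

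If the sponsor wants severity emphasis in the primary test, the SAP should define the estimand, fix the constant and any rescaling, and specify a robust variance. It should also show type I error control by simulation or permutation, and recompute power for that test. An unweighted ordinal primary analysis would also be coherent, but only with the hypothesis and power rewritten to match.

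The cost is a few sentences in Section 5.5, matching edits in Sections 5.4 and 5.7 where the primary model is replicated or checked, and simpler code; no new data are needed. The price is that gradations of severity other than the NMI ≥ 3 cut leave the primary test. For an across-the-board benefit, power at 0.025 is about 67–77% rather than the 96–100% of an unweighted ordinal model. Between 1,231 × 0.020 ≈ 25 and 1,453 × 0.023 ≈ 33 severe infants are expected in the prospective arm, so the covariate list should stay as short as the three now planned.
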